## 6.2.1.2 PrEP Comparison Component Maternal Antepartum Week 4, 8, 12 (during pregnancy)

The Antepartum (AP) Week 4, 8 and 12 visits are targeted to take place on Study Days 28, 56 and 84 respectively, counted from the date of study entry as Day 0, with an allowable window of  $\pm 7$  days. A negative rapid HIV test result at each visit must be available, for participants in Cohort 1 and Cohort 2/Step 2, prior to prescribing study drug.

In addition to the standard of care HIV prevention package provided and routine safety evaluations for all study participants at these visits, adherence and acceptability assessments are performed in Cohort 1.

Participants in Cohort 1 and Cohort 2 may deliver prior to completion of the AP Week 8 or Week 12 visit. If so, evaluations indicated for the AP Week 8 and Week 12 visit should be conducted in addition to the evaluations required for the Maternal Labor and Delivery Visit (Week 0) ([Section 6.2.1.4](#)). In those cases, the visit window of the L&D visit (+14 days) will apply.

Note that women who are selected for and consent to participation in the Qualitative In-Depth Interview during pregnancy may be scheduled for their interview at or after the Week 12 visit. See [Section 6.2.1.8](#) for details about this visit.

PrEP Comparison Component Maternal AP Weeks 4, 8 and 12 ( $\pm 7$ days)		
Behavioral and Counseling		
 
CASI and COVID-19 questionnaire [see Section 6.16]
 
 
Week 12:
 
 
Qualitative IDI Visit [see Section 6.2.1.8]
 
 
Cohort 1 and Cohort 2/Step 2 only:
 
 
iNSC with drug level feedback [see Section 5.3.2]
 
 
Cohort 2 only:
 
 
iNSC [see Section 5.3.2]
 
Assess for social harms [see Section 13.6]
 

Clinical		
 
Obtain interim medical/medications history
 
Perform targeted physical exam
 
Identify/review/update adverse events
 
Perform additional evaluations per Section 8 and/or if clinically indicated (consult CMC if indicated)
 

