#### 6.2.1.4 PrEP Comparison Component Maternal Labor and Delivery Visit

*Note: The calendar will reset after delivery for postpartum visits, with the delivery date considered as Day 0, and subsequent visits calculated from this date.*

The maternal labor and delivery visit will be conducted within 14 days of delivery. If the delivery visit is conducted within 30 days of the last visit, procedures do not need to be repeated except for the rapid HIV test, HIV RNA test and plasma storage for future resistance testing. If the mother does not deliver a live born infant the mother should still complete the Delivery Visit and all subsequent postpartum visits if she is willing to do so.

PrEP Comparison Component Maternal Labor and Delivery Visit Procedures (L/D +14 days)	
Administrative and Regulatory	

Review locator information

Behavioral and Counseling	

Qualitative Interview IDI Visit: to take place at the L/D visit or at an alternative date [see Section 6.2.1.8]

 
Cohort 1 and Cohort 2/Step 2 only:
 

iNSC with drug level feedback [see Section 5.3.2]

 
Cohort 2 only:
 

iNSC [see Section 5.3.2]

Assess for social harms [see Section 13.6]

Clinical	

Obtain interim medical/medications history, including pregnancy outcome

Perform targeted physical exam

Identify/review/update adverse events

Perform additional evaluations per Section 8 and/or if clinically indicated (consult CMC if indicated)

Laboratory	Blood 
Collect blood for:
 

HIV RNA test

Store plasma for HIV drug resistance testing

Rapid HIV test [see Section 6.3 in the event the test is (+)]

TFV- DP level (DBS)

ALT, Creatinine, and CrCl

Other	Radiology 
DXA scan of:
 

Hip

Lumbar Spine

Study Product	
Cohort 1 and Cohort 2/Step 2 only:	

Prescribe and dispense study drug

	

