 DBS sampling is required for Cohort 1 and Cohort 2/Step 2 and Cohort 2; this requirement for Cohort 2 is to confirm and document the absence of PrEP exposure.

#### 6.2.1.5 PrEP Comparison Component Maternal Postpartum Week 6

The PP Week 6 visit will be conducted six weeks ( $\pm$  14 days) following the delivery date.

PrEP Comparison Component Maternal PP Week 6 Visit Procedures (Week 6 $\pm$ 14 days)	
Behavioral and Counseling	
Cohort 1 and Cohort 2/Step 2 only:
 

iNSC with drug level feedback [see Section 5.3.2]

 
Cohort 2 only:
 

iNSC [see Section 5.3.2]

Assess for social harms [see Section 13.6]

PrEP Comparison Component Maternal PP Week 6 Visit Procedures (Week 6 ± 14 days)			
Clinical		
 
• Obtain interim medical/medications history
 
• Perform targeted physical exam
 
• Identify/review/update adverse events
 
• Perform additional evaluations per Section 8 and/or if clinically indicated (consult CMC if indicated)
 
	
Laboratory	Blood	
Collect blood for:
 
 
• HIV RNA test
 
• Store plasma for HIV drug resistance testing
 
• Rapid HIV test [see Section 6.3 in the event the test is (+)]
 
 
Cohort 1 and Cohort 2/Step 2 only:
 
 
• TFV-DP level (DBS)
 
	
	Other	
Collect vaginal swab for:
 
 
• Microbiome
 
 
Collect rectal swabs (if consented) for:
 
 
• Microbiome
 
 
Cohort 1 and Cohort 2/Step 2 only:
 
 
• Collect vaginal secretions for drug level
 
	
Study Product		
Cohort 1 only and Cohort 2/Step 2 only:
 
 
• Prescribe and dispense study drug
 
	

#### 6.2.1.6 PrEP Comparison Component Maternal Postpartum Week 14

The PP Week 14 visit will be conducted 14 weeks (±14 days) following the date of delivery.

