#### ***PrEP Comparison Component:***

All maternal participants will be prescribed once daily FTC/TDF. Visits will occur at Weeks 4, 8, 12 and then every 12 weeks (while pregnant) as well as the time of delivery, and 6, 14, and 26 weeks post-delivery. At each of these visits DBS specimens will be collected for analysis.

The goal for the PrEP Comparison Component is to use the expected TFV-DP levels in DBS from PK Component to define a threshold for optimal adherence. This threshold will be incorporated into the study-specific MOP for the PrEP Comparison Component. This threshold may be the 25th percentile of six or more doses per week on average, which would be 6/7ths of expected level determined in the PK Component. The percentile used (i.e. 25th percentile versus median, etc.) will be determined by the CMC team (described above) and will be based upon the variability in the TFV-DP concentrations in the PK component.

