6.3 Primary Estimand(s) - PrEP Comparison Component

6.3.1 First Primary Estimand

Primary Objective 1: To characterize PrEP adherence among HIV-uninfected young women during pregnancy and for twenty-six weeks postpartum, when provided with enhanced adherence support through mobile technology and counseling based on observed drug levels.	
Estimand description	The probability that pregnant and postpartum HIV-uninfected women will have optimal adherence to daily oral PrEP 1) at defined timepoints; 2) during pregnancy and postpartum (through twenty-six weeks) as measured in TFV-DP concentration levels in dried blood spots during periods when women are formally prescribed PrEP

Treatment	
 1. Daily oral PrEP (200 mg FTC/ 300 mg TDF) during pregnancy and/or postpartum. 2. Enhanced adherence support, including SMS messaging and feedback of drug levels with tailored counseling. 3. Behavioral HIV risk reduction package
Target population	Analysis set
Women who are pregnant and HIV-uninfected, 16-24 years of age, with a confirmed singleton pregnancy of 32 weeks' gestation or less and who have access to a mobile phone, are able to receive and read SMS messages, and express willingness to take PrEP anytime between pregnancy and 26 weeks postpartum	Adherence set: Women initiating PrEP
Variable(s)	Outcome measure(s)
TFV-DP drug concentration level	
 1. TFV-DP drug concentration level from Dried Blood Spots (DBS) measured in pregnancy at 4, 8, 12, 24, 36 week study visits, Labor and Delivery, and postpartum at 6, 14, and 26 week study visits during the periods that participants are receiving PrEP. A binary indicator, "optimal adherence" will be defined as TFV-DP levels meeting or exceeding the threshold of consistent dosing of PrEP ("Green Zone") determined in the PK Component (Appendix Tables 1-2). For women who are pregnant the threshold is 600 fmol/punch if on PrEP \leq 6 weeks and 650 fmol/punch if $>$ 6 weeks; for women who are not pregnant the threshold is 700 fmol/punch if on PrEP \leq 6 weeks and 1050 fmol/punch if on PrEP $>$ 6 weeks. 2. Visits with optimal adherence according to TFV-DP level during pregnancy and during postpartum
Handling of intercurrent events	Handling of missing data

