
 • Failure to start PrEP (in Cohort I or Cohort 2/Step 2) (Treatment policy strategy) • Discontinuation of PrEP: Only visits occurring prior to discontinuation of PrEP will be included. (While on treatment strategy) • HIV seroconversion: Only visits occurring up to the later of the date of first positive HIV test or date when PrEP is discontinued will be included. (While on treatment strategy) 	
Missing data could occur in the following situations:
 
 • Missing visit(s) when adherence would have been assessed • Missing drug concentration results due to sample collection or processing issues. 
Visits without adherence data will be excluded. Sensitivity analyses will be conducted imputing "suboptimal adherence" for each missed visit/concentration result

Population-level summary measure	Analysis approach

 1. Probability of optimal adherence according to TFV-DP levels in DBS at defined times during pregnancy and postpartum 2. Probability of optimal adherence while pregnant and up to 26 weeks postpartum 	
 1. At each visit that TFV-DP levels are obtained, the binomial proportion of women with optimal adherence will be calculated bounded by an exact (Clopper-Pearson) 95% confidence interval. 2. The binomial proportion of visits with optimal adherence in pregnancy and postpartum periods during periods when women are

	formally prescribed PrEP will be calculated with exact (Clopper-Pearson) 95% confidence intervals.
--	--

Supplemental Analyses:

- Exploratory longitudinal analyses identifying baseline and time-varying predictors of optimal adherence will be conducted with multivariable regression models which account for repeated measures across time for each participant.
- Adherence (as measured in TFV-DP levels) will also be summarized as a continuous outcome measure (median, IQR and mean [SD]) at each time point noted above when drug levels are measured, and “average” drug concentrations across pregnancy and postpartum periods, will be calculated, using generalized estimating equations as appropriate. Log transformation of this outcome will be considered if the distribution is not normal.

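### The protocol contradicts itself on whether a delivery drug-level sample is needed within 30 days of the last visit, and the SAP's missing-data sensitivity analysis would score a permitted omission as suboptimal adherence

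*Protocol*

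**What the plan says.** Protocol 6.2.1.4 (Maternal Labor and Delivery Visit) has a no-repeat rule for a delivery visit held "within 30 days of the last visit, procedures do not need to be repeated except for the rapid HIV test"; the list of exceptions ends with "HIV RNA test and plasma storage for future resistance testing". TFV-DP is not on the list.

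Three other places call for the sample and mention no 30-day rule:
- the footnote to the same visit table: "DBS sampling is required for Cohort 1 and Cohort 2/Step 2 and Cohort 2";
- Protocol 10.2, which lists the time of delivery among the visits and adds: "At each of these visits DBS specimens will be collected for analysis";
- Appendix IIA, which shows a 4 mL TFV-DP draw at L&D.

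SAP 6.3.1 makes delivery an adherence time point, with concentrations "measured in pregnancy at 4, 8, 12, 24, 36 week study visits, Labor and Delivery". Its main rule for missing data is: "Visits without adherence data will be excluded". Its sensitivity analysis works by "imputing 'suboptimal adherence' for each missed visit/concentration result". The SAP names two sources of missing data: missed visits, and results lost to collection or processing problems. A sample that the protocol allows a site to skip is not named.

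For women who deliver before AP Week 8 or 12, Protocol 6.2.1.2 says the "evaluations indicated for the AP Week 8 and Week 12 visit should be conducted in addition to the evaluations required" at the delivery visit, within the delivery window. For women on PrEP those evaluations include DBS. SAP Section 4 sets analysis windows of 14 days either side of AP Weeks 4, 8 and 12, and up to 21 days postpartum for delivery.

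**The concern.** A woman whose delivery visit falls within 30 days of her last visit may have no delivery result because the site followed the no-repeat rule, not because she stopped taking tablets. The sensitivity rule has no exception for her, so the result would be scored as non-adherence. The planned check on missing adherence data would then partly measure scheduling. A drop between the main and sensitivity results could be misread as fragility of the adherence estimate.

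The second issue is labelling. When delivery comes before AP Week 8 or 12, a specimen taken at the merged visit can lie inside both an antepartum window and the delivery window. Neither document says which visit it counts for. The label can matter: beyond 6 weeks on PrEP, the optimal threshold in SAP 6.3.1 is 650 fmol/punch for pregnant women and 1050 for women who are not pregnant. A post-delivery value from 650 to 1049 could therefore change category if the visit label decides which threshold applies.

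**Working it through.** **Reproducing the plan's own figure.** Protocol Table 8 gives 68-81% for 75% adherent with n = 200. The exact Clopper-Pearson interval for 150/200 is 68.4-80.8%, which agrees.

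**Effect of imputing.** With p the true proportion optimal and w the share of delivery samples omitted with permission, the imputed proportion is p × (1 − w). For 200 women and p = 75%:
- w = 10%: 135/200 = 67.5% (95% CI 60.5-73.9)
- w = 25%: about 112/200 = 56.0% (48.8-63.0)

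The second interval lies wholly below the Table 8 interval.

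**How large w could be.** The documents do not give it, so these inputs are assumed: entry spread evenly over 14-32 weeks; delivery normal with mean 39.2 weeks and SD 12 days; delivery visit uniform over 0-14 days after delivery (the protocol window); antepartum visits on schedule at days 28, 56, 84, 168 and 252 (Protocol 6.2.1.2 and 6.2.1.3); and full use of the permission. Simulation gives:
- delivery visit within 30 days of the last visit: 46.0% of women;
- of these, women who delivered before AP Week 12: 20.3 points. They still owe the Week 12 evaluations, including DBS, at the delivery visit, so they are removed;
- remaining: w = 25.6%.

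Then:
- proportion optimal at L&D: 0.75 × (1 − 0.256) = 0.558, about 56%;
- pooled pregnancy proportion, at about 3.8 pregnancy samples per woman including delivery: 0.75 × 0.256 / 3.8 = 0.051, a fall of about 5 points.

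**Range.**
- Delivery visit always on the day of delivery: w = 32%, L&D 51%. Always at day 14: w = 19%, L&D 61%.
- Entry at 20-32 weeks: w = 27%. Entry at 10-30 weeks: w = 32%.
- Take-up of 25%: 0.75 × (1 − 0.25 × 0.256) = 70%. Take-up of 10%: 0.75 × (1 − 0.10 × 0.256) = 73%.

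**Overlapping windows.** The AP Week 8 window is days 42-70 from entry and the Week 12 window days 70-98; neither is stated to end at delivery. Under the same assumptions about 27% of women deliver before Week 12. About 16% do so and have a delivery visit inside the Week 12 window; the figure for Week 8 is about 6%. The Week 8 and Week 12 windows themselves meet only on day 70.

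**The case against.** The strongest reply is that the sample is not waived at all. The no-repeat rule is general and permissive and does not mention DBS, while the footnote, Protocol 10.2 and Appendix IIA ask for the sample outright. Sites may well collect it every time, and then nothing is lost. This is a fair reason not to say that the protocol simply waives the delivery sample, which a reader of 6.2.1.4 alone might infer. It does not remove the conflict: none of the three places refers to the 30-day rule, and 6.2.1.4 lists the blood tests that survive it without DBS.

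A second reply is that a permitted omission is not among the SAP's named sources of missing data, so the SAP does not clearly order the imputation. That is correct, but the imputation wording covers each missed concentration result and has no exception. SAP Section 7 plans to report visits missed when an adherence assessment was expected, yet does not define expected or carry the idea into the imputation.

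Third, the main estimate is untouched, and the supplemental continuous, ordinal and other-cutpoint summaries are planned as well. Both points stand. The imputation is the only missing-data sensitivity analysis for adherence, not the only supporting analysis.

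Fourth, a reader might infer that one delivery specimen is to be counted as the Week 8, Week 12 and L&D result. No text says so: Protocol 6.2.1.2 adds evaluations and does not reassign results. A labelling rule may also exist in the Analysis Implementation Plan, to which the SAP assigns coding detail and which is not among these documents. What stands is that the protocol and SAP are silent where windows overlap.

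**Conclusion.** The concern holds as a contradiction within the protocol, combined with a sensitivity rule that can turn a permitted omission into apparent non-adherence. It affects the sensitivity analysis only. With full take-up and the assumed calendar, about 26% of women are affected, a true 75% at delivery appears as about 56%, and the pooled pregnancy proportion falls about 5 points. At 10-25% take-up the delivery figure is about 73-70%. Entry gestation, delivery timing, visit timing and take-up are all assumptions.

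A reader might instead apply the 30-day rule to everyone it reaches: 46% of women, 0.75 × (1 − 0.46) = about 40% at delivery, and 0.75 × 0.46 / 3.8 = about 9 points pooled. The documents do not support that size, because Protocol 6.2.1.2 still calls for DBS in women who deliver before AP Week 12.

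The labelling gap is real but narrower: an unaddressed overlap for about 16% of women at Week 12 under the same assumptions, not an instruction to reuse a specimen.

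**What to change.** 1. Reconcile the 30-day rule in Protocol 6.2.1.4 with its own table footnote, Protocol 10.2 and Appendix IIA, so that the delivery DBS has one stated status. State how the rule works with Protocol 6.2.1.2 when delivery comes before AP Week 8 or 12.
2. In SAP 6.3.1, define which adherence samples are expected under the reconciled schedule and limit the suboptimal imputation to those, so that permitted omissions are not imputed. Use the same definition for the missed-visit report in SAP Section 7.
3. In SAP Section 4 or 6.3.1, give each DBS specimen one visit label by collection date and close the antepartum windows at delivery.

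The cost is a protocol clarification and a few SAP sentences. No new data are needed.

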#### PrEP Comparison Component Maternal PP Week 14 Visit Procedures ( $\pm$ 14 days)

Laboratory	Blood	
Collect blood for:
 
 
• HIV RNA test
 
• Store plasma for HIV drug resistance testing
 
• Rapid HIV test [see Section 6.3 in the event the test is (+)]
 
• ALT, Creatinine, and CrCl
 
• CBC with differential
 
• Pregnancy testing (blood or urine test may be performed)
 
 
Cohort 1 and Cohort 2/Step 2 only:
 
 
• TFV-DP level (DBS)
 

	Urine	
 
• Pregnancy testing (blood or urine test may be performed)
 

Study Product		
Cohort 1 only and Cohort 2/Step 2 only:
 
 
• Prescribe and dispense study drug
 

#### 6.2.1.7 PrEP Comparison Component Maternal Postpartum Week 26: Final Study Visit

The PP Week 26 visit will be conducted 26 weeks ( $\pm$  14 days) following the date of delivery.

If slots are still available for the Qualitative In-Depth Interview and/or if a mother had previously consented to participate at the time of this visit, the in-depth interview may take place during this visit. It is acceptable for the interview to take place on a different date within the Week 26 visit window.

#### PrEP Comparison Component Maternal PP Week 26 Visit Procedures (Week 26 $\pm$ 14 days)

Behavioral and Counseling	
 
• iNSC [see Section 5.3.2]
 
• CASI and COVID-19 questionnaire [see Section 6.16]
 
• Qualitative IDI Visit [see Section 6.2.1.8]
 
• Assess for social harms [see Section 13.6]
 

Clinical	
 
• Obtain interim medical/medications history
 
• Perform targeted physical exam
 
• Identify/review/update adverse events
 
• Perform additional evaluations per Section 8 and/or if clinically indicated (consult CMC if indicated)
 

Laboratory	
Collect blood for:
 
 
• HIV RNA test
 
• Store plasma for HIV drug resistance testing
 
• Rapid test [see Section 6.3 in the event the test is (+)]
 
• ALT, Creatinine, and CrCl
 
• Hepatitis B surface antigen
 
• Syphilis testing
 
• HSV2
 
• Pregnancy testing (blood or urine test may be performed)
 
 
Cohort 1 and Cohort 2/Step 2 only:
 
 
• TFV-DP level (DBS)
 

PrEP Comparison Component Maternal PP Week 26 Visit Procedures (Week 26 ± 14 days)		
	Other	
Collect vaginal swab or urine for:
 
 
• Chlamydia and gonorrhea
 
 
Collect vaginal swab for:
 
 
• Microbiome
 
 
Collect rectal swabs (if consented) for:
 
 
• Microbiome
 
 
Cohort 1 and Cohort 2/Step 2 only:
 
 
• Collect vaginal secretions for drug level
 

	Urine	
 
• Pregnancy testing (blood or urine test may be performed)
 

	Other	
Radiology
 
DXA scan of:
 
 
• Hip
 
• Lumbar Spine
 
 
Note: Pregnancy test required within 14 days prior to DXA scan.

	Study Drug	
Cohort 1 and Cohort 2/Step 2 only:
 
 
• Collect study drug
 

#### 6.2.1.8 PrEP Comparison Component Maternal: Qualitative In-Depth Interview Visit

A subset of women from both cohorts of the PrEP Component will be invited to participate in the Qualitative In-Depth Interviews. The primary activity for this evaluation will be a single in-depth interview which will be audio-recorded and transcribed. All women in this subset must provide written informed consent prior to participating.

Up to 30 antepartum women and up to 30 postpartum women will be selected and interviewed. For Cohort 1, DBS results from two consecutive visits will be reviewed to categorize maternal participants as adherent or not prior to selection; up to ten antepartum women and up to ten postpartum women in each adherence category will be selected. Cohort 2 is comprised of women who declined PrEP.

The timing of the interviews will differ according to pregnancy status and Cohort, as below:

- For pregnant women in Cohort 1 (n=20) – after review of DBS results obtained between Week 12 and delivery.
- For pregnant women in Cohort 2 (n=10) – at or after the Week 12 visit and prior to delivery.
- For postpartum women in Cohort 1 (n=20) – after review of Week 14 DBS results and prior to study exit.
- For postpartum women in Cohort 2 (n=10) – at or after Week 14 and prior to study exit.

All interviews explore experiences around decision making around use of PrEP, which include PrEP start and experiences with taking PrEP over time (Cohort 1) and reasons PrEP was declined (Cohort 2). Experiences with PrEP from a socio-ecological perspective will be discussed and factors related to PrEP drug, self-perceptions of HIV exposure risk and need for PrEP, self-administration/dosing, community influence, experiences at site and structural supports or challenges will be explored.

Interview topics may include how women incorporated daily pill-taking into their daily routines, where they stored PrEP, and whether they disclosed their PrEP use with family members, peers, and their partner(s), and experiences with side-effects for Cohort 1. Women may also be asked

questions regarding the impact of COVID-19 on their study participation, including PrEP adherence and acceptability.

Among women who declined PrEP (Cohort 2), interview topics include factors that were associated with not initiating PrEP, including risk perception, personal and community beliefs about PrEP, and challenges related to COVID-19 that may have influenced PrEP decision making, and opinions about appropriateness of PrEP for other expecting or nursing women in the community.

Interview guides used during the interviews will be developed using reviews of local literature and community advisory board (CAB) feedback. Local researchers/ethnographers will conduct all qualitative interviews with oversight from the study staff. All interviews will be audio-recorded and transcribed and translated into English by trained study staff. Coding will identify main themes emerging from each of the areas explored in the interview.

